Cover Page

Project RESIST: Evaluating the Effects of Anti-smoking Inoculation Messages Among Young Adult Sexual Minority Women

NCT05499520

Date July 5 2024

PROTOCOL TITLE: Project RESIST: Evaluating the Effects of Anti-smoking Inoculation Messages Among Young Adult Sexual Minority Women

Brief Background

This study is the second of two randomized controlled experiments within Project Resist. The first randomized controlled experiment evaluated the effects of LGBTQ-tailoring (using a campaign logo with LGBTQ+ Pride colors and a slogan indicating the campaign's focus is LGBTQ+ health) vs. a control condition (yellow campaign logo and a slogan indicating the campaign's focus is on health in general) on intentions to quit smoking (among current smokers only), intentions to purchase cigarettes, marketing receptivity, industry beliefs, and industry attitudes (both current and non-current smokers). The messages used highlighted anti-tobacco industry arguments (e.g., how the tobacco industry targets children) and health impacts of cigarette smoking (e.g., risks of smoking related illnesses). Results from this experiment have been reported ([NCT04812795](#) and [publication](#)).

In this experiment, we conducted a national online survey experiment among young adult cisgender and transgender SMW smokers and non-smokers to evaluate the effects of exposure to anti-tobacco-industry inoculation health messages that are tailored for LGBTQ+ audiences. We varied the dose (3 messages vs. single message vs. no message), latency (immediate vs. 1-week delay and 1-month delay), and boosters (3 weekly boosters vs. a single dose) of anti-smoking messages on smoking and quitting intentions. Participants were randomized to one of 9 experimental arms using a fractional factorial design. All messages used LGBTQ+ tailored messages and highlighted anti-tobacco industry arguments. Six of the 12 messages used were identical to those used in the first experiment described above and six messages were new messages that were created.

Study Hypotheses

We hypothesize that multiple exposures (3 vs. single), delayed exposure (1-week or 1-month vs. immediate), and booster exposures (3 boosters vs. none) of anti-tobacco industry inoculation health messages will be associated with increased resistance to marketing, reduced smoking susceptibility, reduced intention to purchase cigarettes, and increased quitting intention.

Sample Enrollment

[figure not shown]
This study recruited young adult sexual minority women (SMW), ages 18-30 years, those who current smoke ($n = 1075$) and those who did not smoke ($n = 1516$). Participants were recruited through a combination of the Prolific online panel (~62% of the sample), The Population Research in Identity and Disparities for Equality (PRIDE) Study (~13%), social media advertising (paid Instagram ads and posting through LGBTQ+-serving community organizations' social media accounts) (~14%), and a dating app (HER) (~11%). Participants were asked to complete a baseline survey and then randomized to one of the 9 message conditions (see Experimental conditions table below). **Figure 1** summarizes the CONSORT flow diagram.

Our planned targeted enrollment was to recruit 1500 participants who currently smoke and 1500 who did not currently smoke (total $n=3000$). We used GPower (ver. 3) to estimate the effect sizes in the outcome variables as a function of message condition, assuming two-tailed tests, with 80% power and $\alpha=0.05$, and factored in 20% attrition among participants to arrive at the sample size of 3000.

However, we experienced difficulty in recruiting participants who currently smoke. Recruitment began in September 2022 and concluded in July 2023. In order to address slow recruitment for current smokers, we expanded the recruitment timeline, reached out to over 30 LGBT organizations to canvass over Pride month, flyering ads locally, advertised on social media and on the HER dating app. We further re-opened

the recruitment on the Prolific panel (having enrolled there ~6 months prior) and only received a handful of eligible cases so we ultimately decided to close out the recruitment to focus on the analysis for the remainder of the study.

Figure 1. CONSORT Flow Diagram

Study Protocol

Participants completed the study using the Qualtrics online survey platform. Participants were first screened for eligibility (ages 18-30, identify as sexual minority, and identify as women). We included all individuals who identified as women (cisgender and transgender), as we anticipated that all SMW would be the intended audience of future iterations of ads from this work. Transfeminine populations are currently and traditionally underrepresented in health research, and we did not wish to further marginalize this group by excluding them from participating in this study. Eligible participants completed questions on their baseline outcome measures and characteristics prior to randomization. They were randomly assigned using the Qualtrics built-in randomizer function to one of the nine experimental conditions. **Table 1** provides details of each experimental condition including the sequence of viewing inoculation messages, threat message, and outcomes assessment. We used block randomization to achieve balance across the two conditions based on sexual orientation and race/ethnicity. One month after the baseline survey, participants were invited to complete a follow-up survey to measure the study outcomes and additional questions on participants' characteristics. Depending on the source of enrollment, participants received up to \$12-15 in rewards or gift cards if they completed all phases of the study. The University of Pennsylvania's Institutional Review Board reviewed this study and considered it exempt.

Table 1. Experimental Conditions

No Intervention: No Message Condition

Participants will receive no anti-smoking messages. They will receive the threat message during the baseline survey. Outcomes will be measured before and immediately after seeing the threat message, and at 1 month.

Experimental: Single Message Immediate

Participants will receive a single anti-smoking message followed by the threat message during the baseline survey. Outcomes will be measured before seeing the anti-smoking message and threat message, immediately after seeing the threat message, and at 1 month.

Experimental: Single Message 1 Week Delay

Participants will receive a single anti-smoking message during the baseline survey, followed by the threat message one week later in a separate survey. Outcomes will be measured before seeing the anti-smoking message at baseline, immediately after seeing the threat message at 1 week, and at 1 month.

Experimental: Single Message 1 Month Delay

Participants will receive a single anti-smoking message during the baseline survey, followed by the threat message one month later in a separate survey. Outcomes will be measured before seeing the anti-smoking message at baseline, and immediately after seeing the threat message at 1 month.

Experimental: Single Message 1 Month Delay, Repeated Exposure

Participants will receive a single anti-smoking message during the baseline survey, followed by the threat message one month later. Participants will also receive repeated exposures of a single anti-smoking message at 1, 2, and 3 weeks in separate surveys. Outcomes will be measured before seeing the anti-smoking message at baseline and immediately after seeing the threat message at 1 month.

Experimental: Three Messages Immediate

Participants will receive three anti-smoking messages, followed by the threat message during the baseline survey. Outcomes will be measured before seeing the anti-smoking messages and threat message, immediately after seeing the threat message, and at 1 month.

Experimental: Three Messages 1 Week Delay

Participants will receive three anti-smoking messages during the baseline survey, followed by the threat message one week later in a separate survey. Outcomes will be measured before seeing the anti-smoking messages at baseline, immediately after seeing the threat message at 1 week, and at 1 month.

Experimental: Three Messages 1 Month Delay

Participants will receive three anti-smoking messages during the baseline survey, followed by the threat message one month later in a separate survey. Outcomes will be measured before seeing the anti-smoking messages at baseline, and immediately after seeing the threat message at 1 month.

Experimental: Three Messages 1 Month Delay Repeat Exposure

Participants will receive three anti-smoking messages during the baseline survey, followed by the threat message one month later. Participants will also receive repeated exposures of three anti-smoking messages at 1, 2, and 3 weeks in separate surveys. Outcomes will be measured before seeing the anti-smoking messages at baseline and immediately after seeing the threat message at 1 month.

[figure not shown]
Anti-smoking ads and pro-smoking ads used.

In this experiment (Aim 3 of Project Resist), we conducted a national online survey experiment among young adult cisgender and transgender SMW who smoke and who did not smoke to evaluate the effects of exposure to anti-tobacco-industry inoculation health messages that are tailored for LGBTQ+ audiences. We varied the dose (3 messages vs. single message vs. no message), latency (immediate vs. 1-week delay and 1-month delay), and boosters (3 weekly boosters vs. a single dose) of anti-smoking messages on smoking and quitting intentions. Participants were randomized to one of 9 experimental arms using a fractional factorial design. All messages used LGBTQ+ tailored messages and highlighted anti-tobacco industry health messages (e.g., Let's come together as a community and say no to big tobacco. They've targeted us enough.)

We only used LGBTQ+ tailored messages because we did not design this study to compare effects between culturally tailored versus non-tailored messages that were also used in the experiment in Aim 2 of Project Resist. Similarly, we focused on anti-industry messages and did not use messages that described health effects of smoking which were included in Aim 2 of Project Resist, as we did not design this study to compare the effects between anti-tobacco industry versus health effects messages. Prior inoculation health campaigns and studies have also utilized anti-tobacco industry health messages as experimental message stimuli. Six of the 12 messages used in this experiment were identical to those used in the first experiment (Aim 2 of Project Resist) and six messages were new messages that were created to include an anti-tobacco industry health message and a matching picture.

For those who currently smoke, the bottom of each message included the study project logo (Project Resist), a campaign slogan (e.g., LGBT+ health is our focus), a box stating “Text QUIT to 47848”, a QR code that is linked to the SmokefreeTXT website, and text stating “Find out more about the harmful effects of smoking”. For those who did not smoke, the bottom of each message included the study project logo (Project Resist), a campaign slogan (e.g., LGBT+ health is our focus), a QR code that is linked to the CDC’s website on harmful health effects of smoking, and text stating “Find out more about the harmful effects of smoking”. **Figure 2** shows examples of the anti-smoking messages used for those who smoke and those who did not smoke.

Figure 2 Anti-Smoking Ads

A. For those who currently smoke

B. For those who did not currently smoke

[figure not shown]
[figure not shown]
The 12 anti-smoking messages were randomly grouped into 4 blocks of 3 messages. The rationale for grouping into 4 blocks of messages is to ensure that the two experimental conditions that will receive the repeated exposures (either 1 message per week or 3 messages per week) would receive unique messages each week without any repetition of messages.

- For participants in the single-message and repeated exposure condition, the 4 blocks of messages were randomly ordered for each week and 1 message from each block was randomly selected, with no repetition, to be shown to the participants each week. These participants saw 4 unique messages over the 1-month period.
- For participants in the 3-message and repeated exposure condition, the 4 blocks of messages were randomly ordered for each week and all 3 messages from each block were shown in random order to the participants each week. These participants saw 12 unique messages over the 1-month period.
- For participants in the other single-message conditions with no repeated exposure, 1 block of messages was randomly selected and 1 message from this block was randomly selected and shown to the participants. These participants viewed only 1 message at baseline.
- For participants in the other 3-message conditions with no repeated exposure and viewed 3 message at baseline, 1 block of messages was randomly selected and 3 messages within this block were shown in random order to the participants. These participants viewed 3 unique messages at baseline.

Two pro-smoking ads were selected from the repository, *Trinkets and Trash*, including a Newport menthol cigarette ad that had been shown in LGBTQ+ magazines and a Natural American Spirit ad that used terms such as “freedom to love” and “freedom to marry” to target LGBTQ+ audiences. One ad was randomly selected to be shown to participants as the threat stimulus. **Figure 3** shows the two pro-smoking ads used in this study.

- For participants in the no-message condition, they did not view any anti-smoking message at baseline. They were shown 1 pro-smoking ad and the post-exposure outcome measures were collected immediately.
- For participants in the single-message and 3-messages immediate conditions, they viewed the anti-smoking messages, followed by the pro-smoking ads, and the post-exposure outcome measures were collected immediately.
- For participants in the single-message and 3-messages and 1-week delay conditions, they viewed the anti-smoking messages at baseline. They received the pro-smoking ad 1 week later, and the post-exposure outcome measures were collected at 1 week.
- For participants in the single-message and 3-messages and 1-month delay conditions, they viewed the anti-smoking messages at baseline. They received the pro-smoking ad 1 month later, and the post-exposure outcome measures were collected at 1 month.

Figure 3. Pro-smoking Ads

Primary Outcome Measures

1. Intention to quit smoking (among people who currently smoke)

We used a 4-item scale on intention to quit smoking at baseline and at follow-up (immediate, one-week and one-month) among current smokers only using four items:

- a. I will make an effort to quit smoking in the next 30 days;
- b. I intend to quit smoking in the next 30 days;
- c. I expect to quit smoking in the next 30 days;
- d. How likely is it that you will quit smoking in the next 30 days. Responses ranged on 7-point Likert-like scales.

Responses were summed to create a scale for intention to quit (range from 4-28), higher scores indicate higher intention to quit.

Note: Intent to quit smoking was not collected after exposure to the pro-tobacco message in the no-message, 1-message, and 3-message immediate conditions among people who currently smoked.

2. Intention to purchase cigarettes

The Juster scale was used to measure intention to purchase cigarettes at baseline and at one-month follow-up. Participants were asked, "How likely are you to purchase cigarettes in the next 6 months?" Responses ranged from 0=No chance, almost no chance (1 in 100) to 10=Certain, practically certain (99 in 100). Higher values reflect higher intention to purchase.

Note: Intent to purchase cigarettes was not collected after exposure to the pro-tobacco message in the no-message, 1-message, and 3-message immediate conditions among people who currently smoked and people who did not smoke.

3. Susceptibility to Smoke Cigarettes (among people who currently do not smoke)

Susceptibility to smoke cigarettes was measured among people who do not currently smoke using four-items:

- a. Have you ever been curious about smoking a cigarette?
- b. Do you think you will smoke a cigarette in the next year?
- c. Do you think that you will try a cigarette soon?
- d. If one of your best friends were to offer you a cigarette, would you smoke it? Responses ranged on 4-point Likert-like scales.

Responses were summed to create a scale for susceptibility to smoke cigarettes (range from 0-12). Higher scores indicate increased susceptibility to smoke cigarettes.

Secondary Outcome Measures

1. Receptivity to marketing

Receptivity to tobacco marketing was measured using 2 items:

- a. Tobacco companies should have the same rights to advertise as other companies.
- b. Are you open to using or wearing something with a tobacco company logo or picture on it? Response options range from 1 (strongly agree) to 5 (strongly disagree)

The scale is a sum of the responses to these items, the scale ranges from 2 to 10, with lower scores indicating greater receptivity to marketing.

2. Tobacco industry attitudes

Attitudes toward the tobacco industry were measured using 3 items:

1. I would like to see cigarette companies go out of business.
2. I would not work for a cigarette company.

3. How much do you like cigarette companies.

Response options for items 1 and 2 were from 1 (Strongly agree) to 5 (Strongly disagree). Response options for item 3 were from 1 (Dislike strongly) to 5 (Like strongly). Response options were summed across these 3 items to create the tobacco industry attitudes scale. Values range from 3 to 15, with lower scores indicating stronger anti-industry sentiment.

3. Tobacco industry beliefs

Beliefs about the tobacco industry were measured using 4 items:

1. Cigarette companies lie.
2. Cigarette companies target teens to replace smokers who die.
3. Cigarette companies deny that cigarettes cause cancer and other harmful diseases.
4. Cigarette companies deny that cigarettes are addictive.

Response options were from 1 (Strongly agree) to 5 (Strongly disagree). Responses were summed across these 4 items to create the tobacco industry beliefs scale. Values ranges from 4 to 20, with lower scores indicating stronger anti-industry sentiment.

Statistical Analyses:

Data analysis plan. We will compare covariate distributions across conditions to evaluate the extent to which randomization was successful. Our main analytic strategy is to fit linear regression models to predict the primary and secondary outcomes immediately after exposure to the pro-tobacco message by experimental condition, stratified by smoking status. This regression-based approach allows us to adjust the effect of message condition for factors that may not have been well balanced by randomization (including baseline values of the outcomes), as well as to explore potential interactions between experimental condition and baseline covariates, which can further inform message development. Let Y_i be the outcome (e.g. intention to quit among smokers) for subject i , x_i be the assigned message condition, and c_i be a vector of individual, meso-, and macro-level covariates. We will fit linear regression models of the form

$$\mathbb{E}(Y_i|x_i, c_i) = \alpha + \beta'x_i + \gamma'c_i$$

where β is a vector of coefficients associated with each treatment condition and γ vector of coefficients associated with the covariates. Each $\hat{\beta}$ is interpretable as the average difference in the outcome immediately after exposure to the pro-tobacco message for that treatment condition, vs. the control condition, adjusting for baseline covariates. All planned comparisons will be tested using two-tailed tests at a Bonferroni-corrected $P<0.05$ cutoff.

To account for differential loss to follow-up by treatment arm, we will apply inverse probability of censoring weighting as follows. For each experimental condition, we will estimate the probability of loss to follow-up at the time of the outcome measurement conditional on covariates using logistic regression. Based on these models, we will generate inverse probability of censoring weights and fit weighted models for the primary and secondary outcomes using a generalized estimating equations (GEE) approach. Under the assumption of Missingness At Random (MAR), these models will yield unbiased and consistent estimates of the treatment effects of interest.

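### The hypotheses compare message arms with each other, but the plan defines only arm-versus-control effects and an uncounted Bonferroni family, and for two primary outcomes even those effects cannot be estimated at the stated time point

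*Combined protocol and SAP*

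**What the plan says.** Study Hypotheses sets out three comparisons, all between arms that receive messages: "We hypothesize that multiple exposures (3 vs. single), delayed exposure (1-week or 1-month vs. immediate), and booster exposures (3 boosters vs. none"). The no-message arm appears in none of them.

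The Data analysis plan fits one coefficient per treatment condition, separately by smoking status. Each estimated coefficient "is interpretable as the average difference in the outcome immediately after exposure to the pro-tobacco message for that treatment condition, vs. the control condition". No dose, latency or booster contrast is written down, and the only interactions mentioned are with baseline covariates. On multiplicity it says: "All planned comparisons will be tested using two-tailed tests at a Bonferroni-corrected" 0.05 cutoff. It does not list or count the comparisons, or say whether the family spans outcomes and smoking strata.

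Under Sample Enrollment, the power software was used "to estimate the effect sizes in the outcome variables as a function of message condition, assuming two-tailed tests, with 80% power" and alpha 0.05. No contrast, effect size or corrected alpha is given.

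The Note under the first primary outcome states: "Intent to quit smoking was not collected after exposure to the pro-tobacco message in the no-message, 1-message, and 3-message immediate conditions". The Note under intention to purchase says the same for that outcome, in smokers and non-smokers. Susceptibility, the third primary outcome, carries no such Note.

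**The concern.** The one effect that the plan defines answers a question the hypotheses do not ask, and the questions they do ask have no defined test. Two consequences follow.

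First, a Bonferroni threshold does not exist until the tests are counted. A result with P = 0.01 passes in a family of 4 (threshold 0.0125) and fails in a family of 10 (0.005).

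Second, the plan's time point is just after the pro-smoking ad. For quit and purchase intention the control group was not measured then, so the arm-versus-control coefficient has nothing to be compared with. The contrasts that the plan leaves out (dose among delayed arms, booster) are the ones these data can support.

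**Working it through.** **1. Can the model test the hypotheses?** Label the arms from Table 1: C (no message); 1I, 1W, 1M, 1MB (single message: immediate, 1-week, 1-month, 1-month with boosters); 3I, 3W, 3M, 3MB (three messages, same order). Each coefficient b is that arm minus C. Then:

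- Dose = ¼[(b3I − b1I) + (b3W − b1W) + (b3M − b1M) + (b3MB − b1MB)]
- Latency, 1 week = ½(b1W + b3W) − ½(b1I + b3I)
- Latency, 1 month = ½(b1M + b3M) − ½(b1I + b3I)
- Booster = ½(b1MB + b3MB) − ½(b1M + b3M)

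The control mean cancels in all four. The model can supply them; the plan does not name them.

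**2. Which are estimable just after the ad?**

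| Contrast | Susceptibility | Quit or purchase intention |
|---|---|---|
| 8 arms vs control | yes | none (C missing) |
| Dose | yes, 4 vs 4 arms | delayed arms only, 3 vs 3 |
| Latency, 1 week and 1 month | yes | no (1I, 3I missing) |
| Booster | yes | yes |

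The susceptibility column assumes collection in every arm, since no Note says otherwise.

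**3. How many tests?** Counting hypothesis contrasts only:

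- one outcome (susceptibility): 4
- all primary outcomes and strata: 4 + 2 (quit, smokers) + 2 (purchase, smokers) + 2 (purchase, non-smokers) = 10
- adding secondary outcomes: 3 outcomes × 2 strata × 4 = 24, total 34 (assuming they were collected just after the ad in all arms)

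Per-test alpha is 0.05/4 = 0.0125, 0.05/10 = 0.005 or 0.05/34 = 0.0015. The eight arm-versus-control tests, the set that the text most literally describes, would give 0.05/8 = 0.00625 for one outcome in one stratum.

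**4. Does the sample size reveal the intended contrast?** The planned 3000 cannot be reproduced, because no effect size is stated. Back-solving with equal allocation: 1500 × 0.8 / 9 = 133.3 per arm, and (1.960 + 0.842) × √(2/133.3) = 0.343 SD for one arm against another at uncorrected 0.05. The same 1200 evaluable per stratum would also fit an omnibus nine-arm F test with f = 0.112. The figure does not identify a contrast.

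**5. Illustrative precision.** Detectable difference = (z(1 − α/2) + 0.842) × SE, in SD units at 80% power, with SE = √(2/(a·n)) for a vs a arms. Assumed: equal allocation, 20% loss in every arm, no gain from covariates.

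- Non-smokers: n = 1516/9 × 0.8 = 134.8. Susceptibility at 0.05/4: dose 4 vs 4, 3.339 × 0.0609 = 0.203; latency or booster 2 vs 2, 3.339 × 0.0861 = 0.288. Dose 4 vs 4 in families of 4, 10 and 34: 0.203, 0.222, 0.245. Arm vs control at 0.05/8: 3.576 × 0.1218 = 0.436.
- Smokers: n = 1075/9 × 0.8 = 95.6. Quit or purchase intention at 0.05/2: dose 3 vs 3, 3.083 × 0.0835 = 0.258; booster 2 vs 2, 3.083 × 0.1023 = 0.315.

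Uniform loss overstates loss in C, 1I and 3I, whose post-ad outcome falls in the baseline session. With no loss there (1516/9 = 168.4 per arm), arm vs control at 0.05/8 is 0.41 for a delayed arm and 0.39 for an immediate arm, and latency at 0.05/4 is 0.27.

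**The case against.** The strongest reply is that little is missing. The factor levels are in the hypotheses, every arm is in Table 1, the time point is stated in the analysis plan, and the contrasts are simple combinations of the stated coefficients that may have been among the planned comparisons all along. Much of this stands. It would be wrong to infer that the time point is unstated or that the model cannot test the hypotheses. Boosters exist only at 1-month delay, so the unboosted 1-month arms are the natural comparator. What remains open is whether contrasts are pooled or pairwise, whether the two delays are tested separately, and what the Bonferroni family is.

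A reader might also infer that the dose hypothesis conflicts with the booster arms, because in the three-message booster arm "These participants saw 12 unique messages over the 1-month period" while in the single-message one "These participants saw 4 unique messages over the 1-month period". The documents do not support that: 12 against 4 is the same 3-to-1 dose repeated over four exposures. Pooling is a choice to state and not a contradiction.

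A reader might likewise infer that purchase intention was not collected at 1 week, since its description mentions only baseline and one month. Its Note limits the omission to the no-message and immediate arms, and Table 1 places measurement at 1 week in the 1-week arms. The natural reading is that it was collected, and that the description is loose.

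Finally, Table 1 schedules a 1-month measurement in the no-message, immediate and 1-week arms, so it could be said that a control comparison exists for every outcome. It does, but it is a different estimand: the 1-month survey comes a month after the ad in the no-message and immediate arms, about three weeks after it in the 1-week arms, and straight after it in the 1-month arms.

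**Conclusion.** The point holds and should be fixed before results are reported as tests of the hypotheses. Two parts need no numerical assumption. The three hypotheses have no specified contrast, and the Bonferroni family is uncounted. For two of three primary outcomes, arm-versus-control and latency effects cannot be estimated just after the ad. The second part takes the Notes as the record of what was collected, although Table 1 and the description of the quit scale also list an immediate measurement.

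The open family moves the per-test alpha from 0.0125 to 0.0015, more than eightfold. Under the assumptions shown, this shifts the detectable dose difference for susceptibility only from 0.20 to 0.245 SD. These figures are illustrative. Arm-versus-control and factor contrasts are different estimands, so the figures do not rank their power.

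A reader might infer that the contrasts were chosen after the data were seen. The documents do not show that. Enrolment timing is given as "Recruitment began in September 2022 and concluded in July 2023" and the document is dated July 5 2024, but a list with an earlier date may exist.

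**What to change.** Name linear contrasts of the existing model's coefficients, in the weighted fit as well, as the tests of the hypotheses:

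- **Dose:** three-message minus single-message arms, matched on latency and booster, stating whether the booster pair is pooled with the others.
- **Booster:** the two booster arms minus the two unboosted 1-month arms.
- **Latency:** the 1-week arms, and the unboosted 1-month arms, each minus the immediate arms, noting that time since baseline differs and that no control arm sees the ad after a delay.

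State the Bonferroni family by contrast, outcome and stratum, and label arm-versus-control as a separate family. Merging the two families would lower the per-test alpha.

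For quit and purchase intention just after the ad, list only dose among the delayed arms and booster, and say that arm-versus-control and latency are not estimable. Label any comparison based on the 1-month survey as a different estimand, because time since the ad differs between arms. Tidy the timing sentence for purchase intention so that it agrees with its Note and Table 1.

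Date the list. Unless an earlier dated one exists, label the contrasts as specified after recruitment closed.

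The cost is SAP wording and a few contrast statements, with no new data. Contrasts first written now cannot be presented as prespecified. Dose-by-latency and dose-by-booster interactions are optional and exploratory. In non-smokers the dose-by-booster difference has SE √(4/134.8) = 0.172 and is detectable only at 2.802 × 0.172 = 0.48 SD at uncorrected 0.05, so report it, if at all, as an estimate with a confidence interval.

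### The only stated power (80% at alpha 0.05 for 1500 per smoking stratum) does not describe the tests to be run: 1075 smokers were enrolled, and testing uses a Bonferroni cutoff with no stated divisor

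*Combined protocol and SAP*

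**What the plan says.** All references are to the combined protocol and SAP.

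- **Sample Enrollment, target.** "Our planned targeted enrollment was to recruit 1500 participants who currently smoke and 1500 who did not currently smoke". GPower was used "to estimate the effect sizes in the outcome variables as a function of message condition, assuming two-tailed tests, with 80% power and" alpha 0.05, and the authors "factored in 20% attrition among participants to arrive at the sample size of 3000". No effect size, standard deviation, test or contrast is given, and no multiplicity correction is mentioned.
- **Sample Enrollment, achieved.** 1075 smokers and 1516 non-smokers. The shortfall is acknowledged ("However, we experienced difficulty in recruiting participants who currently smoke"), but no power or detectable effect is given for the achieved numbers.
- **Statistical Analyses, Data analysis plan.** Models predict outcomes "by experimental condition, stratified by smoking status", and each coefficient is read "as the average difference in the outcome immediately after exposure to the pro-tobacco message for that treatment condition, vs. the control condition". Then: "All planned comparisons will be tested using two-tailed tests at a Bonferroni-corrected" 0.05 cutoff. The planned comparisons are not listed and the divisor is not given. The models may adjust for baseline covariates, including baseline values of the outcomes.

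**The concern.** The planned figure and the planned tests differ in two respects. Because the strata are modelled separately, the 1516 non-smokers cannot make up for missing smokers. And a Bonferroni cutoff is stricter than 0.05 whenever there is more than one comparison, so a calculation at 0.05 per test overstates power in both strata.

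What is at stake is how a null result is read, above all in smokers. With no effect size stated, no divisor, and a power figure tied to a sample that smokers did not reach, a reader cannot tell what effect the study could have detected. An unlisted family also leaves the significance threshold itself open until someone names it.

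**Working it through.** **Inputs from the document.** Power 80%, two-tailed alpha 0.05, attrition 20%, target 1500 per stratum, enrolled 1075 and 1516, nine arms.

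**Assumptions, not in the document.** Sizing within stratum; equal allocation; the planned 20% loss in every arm; the same contrast in planning and analysis; no precision gain from baseline adjustment beyond planning. Divisors k = 2 and k = 8 are illustrations; 8 corresponds to eight message arms against one control.

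**The plan's own figure.** The total of 3000 cannot be computed forward, because no effect size is given. It can only be solved backwards. For arm against control, n per arm = 1500 × 0.80 / 9 = 133.3, so d = (1.960 + 0.842) × √(2/133.3) = 0.34. This d is a reconstruction, not a figure from the plan.

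**Shortfall.** 1075/1500 = 71.7%. The target implied 1500 × 0.80 = 1200 completers, so enrolment before any loss is already below that. After 20% loss, 860 remain, or 95.6 per arm.

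**Power for the planned effect.** Power = Φ(2.802 × √r − z), where r = enrolled/1500 and z = 1.960, 2.241 or 2.734 for k = 1, 2 or 8. √r is 0.847 for smokers and 1.005 for non-smokers.

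| Stratum | k = 1 | k = 2 | k = 8 |
|---|---|---|---|
| Planned, 1500 | 80% | 71% | 53% |
| Smokers, 1075 | 66% | 55% | 36% |
| Non-smokers, 1516 | 80% | 72% | 53% |

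For example, smokers with k = 1: 2.802 × 0.847 − 1.960 = 0.41, and Φ(0.41) = 66%. The shortfall acts on smokers only; the correction acts on both strata.

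**If planning was unadjusted and the analysis adjusts for baseline.** Replace r by r/(1 − ρ²), where ρ is the baseline-outcome correlation.

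| Stratum | ρ | k = 1 | k = 2 | k = 8 |
|---|---|---|---|---|
| Smokers | 0.5 | 78% | 69% | 50% |
| Smokers | 0.7 | 91% | 86% | 72% |
| Non-smokers | 0.5 | 90% | 84% | 70% |
| Non-smokers | 0.7 | 98% | 96% | 89% |

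Smokers regain 80% at ρ of about 0.53 (k = 1) or 0.64 (k = 2).

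**If 0.05 was a familywise level already split in planning.** The correction then costs nothing further, but the shortfall remains: Φ((z + 0.842) × 0.847 − z) gives smokers 64% for k = 2 and 62% for k = 8.

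**If GPower was run on all 3000.** r = 1075/3000, and smokers have about 39% with k = 1.

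**Detectable effect, arm against control in smokers, 20% loss in both arms.** (1.960 + 0.842) × √(2/95.6) = 0.41 at alpha 0.05, and (2.734 + 0.842) × √(2/95.6) = 0.52 with k = 8, against 0.34 as planned.

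**The case against.** Four objections carry weight.

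1. *The document already presents 80% as a planning figure and reports the shortfall.* This stands. No arithmetic error in 3000 is shown; the defect is that the figure was not restated and its basis is missing.
2. *The planning alpha may have been familywise.* A reader might infer that the calculation used an uncorrected alpha. The text says only 0.05 and is silent on correction, so that cannot be asserted. The divisor is needed on either reading.
3. *Baseline adjustment may restore power.* It may, particularly in non-smokers and with small divisors. The document does not say whether planning already counted on it, so neither full power nor a loss can be taken as established.
4. *Power is of little use once recruitment has closed, and confidence intervals show what a null result excludes.* This is right as to reporting. It does not supply the missing divisor, which sets the significance threshold.

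A reader might also infer that arm-against-control tests do not exist for any smoker primary outcome. Notes under Primary Outcome Measures do say that quit and purchase intention were not collected after the threat message in the no-message and immediate arms. But Table 1 says of the no-message arm that "They will receive the threat message during the baseline survey", with outcomes measured immediately afterwards. The section on the ads used says the same of that arm and the immediate arms, and the quit-intention text lists an immediate time point. The document contradicts itself here, so the inference is not settled. Nor does the plan name a particular set of pooled contrasts as its comparison family.

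**Conclusion.** The point holds as a mismatch between the stated power and the planned tests. The text alone establishes that 1075 of 1500 smokers were enrolled, that the analysis is stratified, that testing is Bonferroni-corrected, and that the divisor, effect size and contrast are absent.

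The size is conditional on the assumptions listed with the calculation. The shortfall alone takes smokers from 80% to about 66%. Any further loss in either stratum depends on the unstated divisor and on whether planning allowed for it. The baseline-adjustment range for smokers runs from 50% (correlation 0.5, divisor 8) to 91% (correlation 0.7, no correction), so loss of power is likely, not certain. Actual loss and allocation by arm may also differ from what is assumed here, because the control and immediate arms see the threat within the baseline survey. The retained numbers should come from the CONSORT diagram, which is not visible in the text reviewed.

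**What to change.** 1. First reconcile the notes under Primary Outcome Measures with Table 1 and the description of the ads, on whether quit and purchase intention were collected after the threat in the no-message and immediate arms. This decides which contrasts can be estimated.
2. Keep 80% as the planned figure. State its effect size and contrast, whether it was per stratum or on 3000, and whether 0.05 was per test or familywise.
3. List the planned comparisons and the Bonferroni divisor by outcome and stratum. Say when they were fixed, and whether that was before outcome data were seen.
4. Give the effect detectable with 80% power in each stratum, at retained numbers per arm and corrected alpha, only for contrasts that exist.
5. Report null results with confidence intervals set against those effects, not with power computed from observed effects.

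The cost is wording and a short table. The stated power will probably look less favourable, and a divisor first stated after recruitment closed will be visibly late.
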